1.0 Objectives

This study plans to address the following hypotheses:

- 1.1 The addition of Ibandronate initiated immediately after the transplantation (21 to 60 days) will prevent bone loss in patients undergoing allogeneic bone marrow transplantation (BMT) with underlying hematologic malignancies or hematological disorders.
- 1.2 BMT patients who require prolonged steroid and other immunosuppressive treatment for Graft versus Host Diseases (GVHD) have a higher rate of bone loss, which can be prevented or attenuated by Ibandronate.

Specific objectives to test these hypotheses are:

a. Primary Objective:

1. To prospectively compare the bone mineral density changes of lumbar spine, femoral neck and total hip between patients randomly assigned to Ibandronate and control group over 12 months post bone marrow transplantation at the University of Texas MD Anderson Cancer Center.

b. Secondary Objectives:

1. To measure and compare the accumulated level of steroid used in both treatment and control groups.
2. To collect and compare the level of serum C-terminal telopeptide (CTX) in both treatment and control groups to monitor the bone turnover rate for the duration of the study.
3. To conduct a cost-effectiveness analysis of participating patients for both outcomes on bone mineral density (measured data) and skeletal-related events (modeled data).
4. To record incidence of bone fractures and the graft rate in both treatment and control groups.

2.0 Background

Bone marrow transplantation (BMT) is performed with increasing frequency and for expanding indications, with the majority of patients surviving for many years. In this context, bone loss is a common and serious post-transplant complication. Bone loss, occurs early and most rapidly during the first three to six months after the transplantation, and is often more severe at the femoral neck (1, 2). The degree of bone loss can be severe enough to cause fractures. Lower

bone mineral density in femoral neck in this population has also been associated with avascular osteonecrosis (3).

Osteoporosis developed after BMT has a complex mechanism involving both the direct effect of the transplanted bone marrow on the stromal cell compartment and the effects from immunosuppressive therapies (3). As a result of the decreased osteoblast and increased osteoclast activity, there is both increased bone resorption and decreased bone formation. After the transplantation, over 50% of BMT patients develop some form of Graft Versus Host Disease (GVHD), which requires prolonged use of glucocorticoid as well as other forms of immunosuppression. In addition, BMT recipients may also experience some bone loss before the transplantation (4), that is related to their underlying disease and the modalities used to treat them. Their prior treatment may result in a variety of effects associated with bone loss, including glucocorticoid-induced decreases in bone formation and serum 1,25-dihydroxyvitamin D₃, or chemotherapy-induced hypogonadism. Therefore patients with hematologic malignancies or hematological disorders undergoing bone marrow transplantation are at high risk of bone loss.

In a prospective, randomized 12-month study of Risedronate on bone mass and bone turnover in patients who had undergone allogeneic BMT at least 6 months before the treatment, spine and femoral neck bone mineral density (BMD) did not change significantly in patients on Risedronate and decreased in those taking placebo (5). However, this study did not answer the question of whether bisphosphonates could prevent the rapid bone loss commonly seen during the first three months post-BMT. In another uncontrolled observational study, three monthly intravenous Pamidronate infusions attenuated femoral neck bone loss in the first six months after allogeneic BMT (2). In a recent randomized, controlled study in patients undergoing allogeneic stem cell transplantation, using Pamidronate initiated before the transplantation decreased the bone loss significantly at the lumbar spine, hip, and the femoral neck. However there was still significant bone loss at the hip and femoral neck that was not completely prevented by pamidronate, warranting the use of a more potent bisphosphonate for more durable maintenance of bone mass after transplantation (6).

Ibandronate (Boniva) has been shown to significantly increase bone mineral density in the lumbar spine and the hip bone in postmenopausal patients. Compared to placebo, Ibandronate taken orally at 150 mg once monthly or 3 mg intravenously quarterly significantly increased bone mineral density and decreased the rate of new vertebral fractures (7). Ibandronate is more potent than other bisphosphonates such as Pamidronate, Risedronate and Alendronate.

So far there is no consensus on how to effectively prevent and treat osteoporosis associated with bone marrow transplantation. As for steroid induced osteoporosis, the American College of Rheumatology Ad Hoc Committee on Glucocorticoid-Induced Osteoporosis recommends obtaining a baseline measurement of bone mineral density at the lumbar spine and/or hip when initiating long-term (i.e., in a dose of 5 mg/day or higher for more than 3 months) glucocorticoid therapy with longitudinal follow ups. The committee also recommends bisphosphonates used in such patients in conjunction with calcium and vitamin D supplementation for the prevention of osteoporosis (8). Such consensus has not been tested in cancer patients receiving BMT.

Although there are known risk factors of osteoporosis associated with bone marrow transplantation and the subsequent immunosuppressive treatment, guidelines for the prevention and effective treatment of bone loss in this high risk population are lacking. Data on whether therapy for osteoporosis treatment or prevention initiated around the time of the transplantation reduces fracture risk after transplantation is limited. Bisphosphonates, in particular, suppress

bone resorption for up to 12 months after discontinuation of therapy. Transplantation with immediate addition of bisphosphonates may prevent the accelerated bone resorption that develops immediately after transplantation and could theoretically mitigate post-transplant bone loss. Moreover, anti-resorptive therapy clearly increased bone mineral density and reduces fracture in other populations, including patients undergoing solid organ transplant. Given such, this proposal is designed for the prevention of osteoporosis in this high risk population.

3.0 Patient Eligibility

The study eligibility requirements will include the following inclusion/exclusion criteria:

3.1 Inclusion criteria:

- 1) Age greater than or equal to 18 years.
- 2) Patients with the diagnosis of hematologic malignancies or hematological disorders, who are immediately post- allogeneic bone marrow transplantation.
- 3) Female patients of childbearing potential (i.e. no hysterectomy, no loss of menses for 12 consecutive months), must be willing to use contraception.
- 4) Negative pregnancy test in premenopausal patients.
- 5) Patients with GVHD or infections can be entered only if they respond to treatment and become controlled.
- 6) Dental considerations: patients with negative dental screening for jaw osteonecrosis 0-3 months prior to their transplant and patients that do not have a plan for tooth extraction in the near future.

3.2 Exclusion criteria:

- 1) Patients with documented relapsed malignancy or recurrence of the original hematological disorder after the transplant, uncontrolled acute GVHD, or uncontrolled infection.
- 2) Patients with hypocalcemia of less than 8.4 (corrected to account for the albumin level).
- 3) Patients with hypercalcemia >12.2 , due to a cause not related to their hematological malignancy or hematological disorder (i.e. hyperparathyroidism, multiple myeloma).
- 4) Hypersensitivity to Ibandronate or other bisphosphonates.
- 5) Pre-existing osteoporosis, defined as a bone density T-score of -2.5 S.D. or less.
- 6) Renal insufficiency (calculated creatinine clearance < 30 ml/min).
- 7) Patients already on bisphosphonates (over the past two years), calcitonin, anabolic steroids, or daily oral fluoride supplement.
- 8) Myeloma patients who have previously been on bisphosphonates over the past two years and/or have active bone lesions.
- 9) If corrected calcium is above 10.3 and the iPTH is elevated or normal, the patient will be excluded from the study.
- 10) Patients with a 25-hydroxyvitamin D concentration <20 ng/ml and evidence of osteomalacia (low ionized calcium and elevated intact PTH).
- 11) Patients with recent tooth extraction with signs of incomplete healing or infection will be excluded.

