4.0 Treatment/study Plan

Patients who had hematological malignancies or hematological disorders and underwent allogeneic bone marrow transplantation are eligible to participate in the study. Members of the research team

will enroll eligible patients who meet the inclusion criteria in the study after obtaining agreement of their transplant physician. Patients with GVHD or infections can be entered only if they respond to treatment and become controlled.

As part of standard care for pre-BMT work up, all patients will have their 25(OH) Vit D levels checked. Patient with vitamin D deficiency (< 20 ng/ml) will be supplemented to adequate level (≥ 20 ng/ml).

Patients will then be randomized into the following two groups: 1) treatment: Ibandronate 3 mg intravenously over 15-30 seconds for 4 doses at 0-1.5, 3, 6, and 9 months free of charge; or 2) control: Patients will only receive daily oral calcium and vitamin D supplements. Patient's prior vitamin D supplement status will be considered as one of the randomization factor. After entering the trial, all patients will receive 500 mg of elemental calcium carbonate and Vitamin D Analog 400 IU orally twice daily for 12 months to be taken at home during the trial. Patients who do not tolerate the calcium pills provided by the trial are allowed to take another brand of calcium/vitamin D at home as tolerated with equivalent dosing. Patients who are still on weekly Ergocalciferol have the option of holding their daily vitamin D 400 IU twice daily and must resume the daily vitamin D when they are off the weekly Ergocalciferol.

BMD at lumbar spine, femoral neck and total hip will be determined at baseline (up to 3 months prior to the transplant or prior to the enrollment), 6, 12 months (± 4 weeks) post transplants for all patients in both groups by DEXA at MDACC. The change of BMD between baseline and 12 months in both Ibandronate treatment and control groups will be summarized and analyzed for statistical significance.

The members of the research team will collect data and/or blood for the following:

1. Bone turnover marker, the serum CTX will be measured at baseline, 3, 6, and 12 months (± 4 weeks)
2. Routine laboratory monitoring includes calcium, magnesium, alkaline phosphatase, albumin, and creatinine at baseline and at 3, 6, 9, and 12 months (± 4 weeks) post-transplant.

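### Exclusion 3 names multiple myeloma as a cause unrelated to haematological malignancy, and its cause clause leaves a narrow route for a patient with disease-related calcium above 12.2 to enter

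*Combined protocol and SAP*

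**What the plan says.** All eligibility rules cited here are in section 3.2 of the combined protocol and SAP.

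- **Item 3** excludes calcium above 12.2 when the hypercalcaemia is "due to a cause not related to their hematological malignancy or hematological disorder (i.e. hyperparathyroidism, multiple myeloma"). No unit is given; I read it as mg/dL.
- **Item 9** is the only other upper calcium rule: "If corrected calcium is above 10.3 and the iPTH is elevated or normal, the patient will be excluded from the study".
- **Item 8** deals with myeloma: "Myeloma patients who have previously been on bisphosphonates over the past two years and/or have active bone lesions".
- **Item 1** excludes, among others, "Patients with documented relapsed malignancy or recurrence of the original hematological disorder after the transplant".

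Inclusion criterion 2 (section 3.1) admits haematological malignancies in general and does not set myeloma apart.

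Section 4.0 then states that "all patients will receive 500 mg of elemental calcium carbonate and Vitamin D Analog 400 IU orally twice daily for 12 months". It allows an equivalent brand for patients who cannot tolerate the trial's pills, and one option to hold: "Patients who are still on weekly Ergocalciferol have the option of holding their daily vitamin D 400 IU twice daily". Neither depends on serum calcium. Calcium and albumin are scheduled at baseline and at 3, 6, 9 and 12 months, each within 4 weeks either way.

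**The concern.** There are two separate points.

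First, item 3 contradicts itself for myeloma. Its test is whether the cause is unrelated to the patient's haematological disease, yet one of its two examples of an unrelated cause is a haematological malignancy that some enrolled patients may have. Two screeners could reach opposite decisions on the same patient.

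Second, for every haematological disease the test itself exempts hypercalcaemia caused by that disease. A patient who entered this way would be assigned calcium and vitamin D supplements while already known to be hypercalcaemic. What is at stake is consistent screening and the safety of an individual patient.

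**Working it through.** No planned figure depends on this item, so there is nothing to reproduce. The check applies the rules to cases.

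**1. Myeloma under item 3.** Take a patient transplanted for myeloma, with calcium above 12.2 due to the myeloma, no bisphosphonates in the past two years and no active bone lesions. Item 8 does not exclude this patient. Under item 3 the cause is related to the patient's malignancy, so the clause says not excluded. The parenthesis lists myeloma as an excluding cause, so it says excluded. If the parenthesis was meant to illustrate related causes instead, hyperparathyroidism is the misplaced example. The item is inconsistent either way.

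**2. Items 3 and 9 together.** Item 3 applies if calcium >12.2 and the cause is unrelated, reading the clause literally. Item 9 applies if corrected calcium >10.3 and iPTH is normal or elevated. Measured and corrected calcium are taken as equal.

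| Calcium | iPTH | Cause | Item 3 | Item 9 | Result |
|---|---|---|---|---|---|
| 12.5 | low | disease-related | no | no | not excluded |
| 12.5 | low | unrelated | yes | no | excluded |
| 12.5 | normal or high | disease-related | no | yes | excluded |
| 12.5 | normal or high | unrelated | yes | yes | excluded |
| 11.0 | low | either | no | no | not excluded |
| 11.0 | normal or high | either | no | yes | excluded |
| 10.0 | any | either | no | no | not excluded |

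Above 12.2, one combination escapes both rules: disease-related cause with low iPTH.

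**3. What else stands in the way.** Item 1 removes the patient only if relapse or recurrence after transplant is documented, so persistent disease, for example, is not covered. Item 8 removes some myeloma patients. Section 4.0 requires the transplant physician's agreement, which is a safeguard but not a calcium criterion.

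**4. Exposure.** Daily dose in either arm: 2 × 500 = 1,000 mg calcium and 2 × 400 = 800 IU vitamin D.

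**5. Time to the next scheduled calcium.** I take 3 months as day 91.
- Entry on days 21 to 45 (Table 1): 91 − 45 = 46 to 91 − 21 = 70 days.
- Entry on days 21 to 60 (hypothesis 1.1, "initiated immediately after the transplantation (21 to 60 days")): 91 − 60 = 31 to 70 days.
- Days 21 to 60 with the 4-week window (day 63 to day 119): 63 − 60 = 3 to 119 − 21 = 98 days.

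Section 4.0 also gives the first dose as 0 to 1.5 months. I did not use that, because the other two places both start at day 21.

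**6. Would an albumin correction help?** Item 2 specifies one ("Patients with hypocalcemia of less than 8.4 (corrected to account for the albumin level")), as does item 9; item 3 is silent. The protocol gives no formula. Assume 0.8 per 1 g/dL of albumin away from 4.0 (range 0.6 to 1.0). The measured value matching a corrected 12.2 is 12.2 − k × (4.0 − albumin).
- Albumin 3.5: 12.2 − 0.8 × 0.5 = 11.8 (11.7 to 11.9).
- Albumin 4.5: 12.2 + 0.8 × 0.5 = 12.6 (12.5 to 12.7).

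If item 3 now means uncorrected calcium, a patient with albumin 4.5, measured calcium 12.3 to 12.6, an unrelated cause and suppressed iPTH would move from excluded to eligible. The correction is not needed for either defect.

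**The case against.** The strongest reply is that the route is close to theoretical. To use the exemption, a screener must attribute calcium above 12.2 to the patient's own disease after transplant. That will usually mean finding the disease active, and items 1, 8 and 9 and the transplant physician then stop most such patients. The myeloma contradiction decides eligibility only for someone who passes all of these. This stands as a limit on size. It does not remove the contradiction or close the route.

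The exemption may also be deliberate: the title of reference 7 lists hypercalcaemia of malignancy among ibandronate's uses. That is a possible reason in the treatment arm, but controls receive only calcium and vitamin D.

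Myeloma could be read as a second disease, distinct from the transplant indication. That is strained, since item 8 treats myeloma patients as candidates.

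A reader might infer more than the text supports:
- *That some hypercalcaemic patients will enter.* The documents give no frequency.
- *That the trial has no safeguard on supplements.* The supplied text has no calcium-based hold, but the appendices were not supplied.
- *That calcium would go unchecked for up to 98 days.* The range covers only tests scheduled by the protocol. Baseline calcium is known, and routine transplant care may test sooner. The interval measures no risk.

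**Conclusion.** Item 3 is wrong as written, and the matter is minor. The myeloma contradiction is plain on the page. The exemption is also real, but confined to disease-related calcium above 12.2 with suppressed iPTH, no documented relapse or recurrence and, for myeloma, neither active bone lesions nor recent bisphosphonates. The number of such patients is unknown, probably very small and possibly zero.

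One might go on to infer that the treatment comparison is compromised. It is not: the criterion is applied before randomisation, both arms receive the same supplements, and neither the sample size nor the primary analysis depends on it.

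The conclusion rests on a literal reading of the cause clause. Whether the exemption was intended, and whether the appendices hold a supplement rule, cannot be settled from the supplied text.

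**What to change.** Reword item 3 as: *Patients with hypercalcemia >12.2 from any cause.* This deletes the cause clause and both examples, and so removes the contradiction and the exemption together. Leave items 1, 8 and 9 unchanged; no PTH-based exclusion is lost. After the change, every 12.5 row in the table is excluded.

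Do not add an albumin correction as part of this amendment, for the reason shown in step 6.

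The cost is a one-line amendment using calcium already measured at baseline, and at most a very few patients become ineligible. The change does not cover patients at 10.3 to 12.2 with suppressed iPTH, who remain eligible whatever the cause.

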4.0 Treatment/study Plan

Patients who had hematological malignancies or hematological disorders and underwent allogeneic bone marrow transplantation are eligible to participate in the study. Members of the research team

will enroll eligible patients who meet the inclusion criteria in the study after obtaining agreement of their transplant physician. Patients with GVHD or infections can be entered only if they respond to treatment and become controlled.

As part of standard care for pre-BMT work up, all patients will have their 25(OH) Vit D levels checked. Patient with vitamin D deficiency (< 20 ng/ml) will be supplemented to adequate level (≥ 20 ng/ml).

Patients will then be randomized into the following two groups: 1) treatment: Ibandronate 3 mg intravenously over 15-30 seconds for 4 doses at 0-1.5, 3, 6, and 9 months free of charge; or 2) control: Patients will only receive daily oral calcium and vitamin D supplements. Patient's prior vitamin D supplement status will be considered as one of the randomization factor. After entering the trial, all patients will receive 500 mg of elemental calcium carbonate and Vitamin D Analog 400 IU orally twice daily for 12 months to be taken at home during the trial. Patients who do not tolerate the calcium pills provided by the trial are allowed to take another brand of calcium/vitamin D at home as tolerated with equivalent dosing. Patients who are still on weekly Ergocalciferol have the option of holding their daily vitamin D 400 IU twice daily and must resume the daily vitamin D when they are off the weekly Ergocalciferol.

BMD at lumbar spine, femoral neck and total hip will be determined at baseline (up to 3 months prior to the transplant or prior to the enrollment), 6, 12 months (± 4 weeks) post transplants for all patients in both groups by DEXA at MDACC. The change of BMD between baseline and 12 months in both Ibandronate treatment and control groups will be summarized and analyzed for statistical significance.

The members of the research team will collect data and/or blood for the following:

1. Bone turnover marker, the serum CTX will be measured at baseline, 3, 6, and 12 months (± 4 weeks)
2. Routine laboratory monitoring includes calcium, magnesium, alkaline phosphatase, albumin, and creatinine at baseline and at 3, 6, 9, and 12 months (± 4 weeks) post-transplant.
3. Other factors affecting bone metabolism will be measured which include 25(OH) Vit D and intact PTH levels at baseline (as part of pre-transplant workup, or prior to the enrollment) and at the end of the trial. If a patient was found to have vitamin D deficiency 3 months prior to the transplant and if a patient had been on weekly Ergocalciferol supplement, the patient will be eligible for this study and their vitamin D supplementation status will be considered as one of the randomization factor. Patient had prior Ergocalciferol supplement are randomized to either treatment or control group following the stratum 1 of the Randomization Scheme, Appendix F. Patients with no prior Ergocalciferol supplement are randomized according to the stratum 2 of the Randomization Scheme, Appendix F.

Sex hormones will be measured at the baseline (± 8 weeks) and the 12 months (± 8 weeks) (Testosterone or Estradiol, FSH and LH). Female patients who have documented laboratory values indicating postmenopausal state prior to the study entry will not be required to have new levels drawn. Female patients whose sex hormone levels showing menopausal state at baseline will not have repeat sex hormone study at the end of the trial. Serum for future research will also

be collected and banked at baseline and at 3, 6, 9, 12 months post transplant for measurements of cytokines and antibodies involved in the metabolism of the bone and the development of GVHD after the trial. Examples of future cytokine measurements may include: Osteoprotegrin (OPG), TNFa, Interleukin-6, GM-CSF, and IGF-1.

4. Incidence of fractures will be radiologically confirmed and compared between the two groups. Graft rate will be collected at 12 months for both groups and analyzed for statistical difference.

5. Data collection for the pharmaco-economic benefit model includes drug and administration costs via patient medical record databases and MDA Cost Accounting System.

Table 1: Summary of Treatment/study Plan

Assessments	1 month (21-45 days)	3 months	6 months	9 months	12 months
Medicine (IV)	x	x	x	x	
DEXA (bone mineral density)	x		x		x
Serum CTX	x	x	x		x
Routine lab : Ca, Mg, albumin, Cr, Alk phos	x	x	x	x	x
25 (OH)VitD, intact PTH, x					x
Sex Hormones Testosterone or Estradiol, FSH and LH (blinded and banked)	x				x
Serum collection for future x testing may include the following examples: Osteoprotegrin (OPG), TNFa, Interleukin-6, GM- CSF, IGF-1 (Banked)		x	x	x	x
Graft rate and Fracture rate					x

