5.0 Statistical Consideration

This is a randomized phase III trial to determine whether the use of Ibandronate significantly decreases the amount of bone loss in patients with BMT, compared to those in the control group. Patients will be equally randomized to control or treatment groups at baseline. All transplant patients will receive oral calcium 500 mg and vitamin D 400 IU twice daily throughout the trial.

The primary endpoint is the percent reduction in bone mineral density (BMD) of the lumbar spine, femoral neck, and total hip measured at 12 month relative to baseline, which we denote here as Diff_BMD. Assuming that the mean Diff_BMD is 12% decrease in the control group and is 0.1% in the treatment (Ibandronate) group, a maximum of 120 patients (60 patients per group)

will be needed in order to have an 80% power to detect this difference at a two-sided significance level of 0.05, assuming a common standard deviation of 0.23. Assuming a drop-out rate of 40% for the patients due to mortality and relapse in the first year, a maximum of 200 patients will be enrolled into the study. The total accrual period will be 20 months, with 10 patients enrolled per month.

Two interim analyses are planned for the primary endpoint of the percent reduction in BMD between baseline and 12 months, when 40 and 80 patients have been accrued into the study and followed for one year, respectively. A Lan-DeMets spending function with O'Brian-Fleming stopping boundaries has been assumed. The two-sided Z-score cut-off values for rejecting the null hypothesis are ± 3.71 and ± 2.51 for the two interim looks, respectively.

The change of BMD between baseline and 12 months will be summarized by treatment and control groups. Data will be transformed as appropriate to satisfy the normality assumption. A two-sample t-test on the transformed data or Wilcoxon rank-sum test will be performed to compare the two groups in terms of percent change of BMD from baseline to 12 months.

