5.2 Safety Monitoring

In addition, a safety monitoring rule will be implemented using the method of Thall, Simon and Estey (1995, 1996). We define the adverse event (AE) as “the percent reduction in BMD is greater than or equal to 15% from baseline to 6 months” and denote its probability as p. The trial will be stopped if, for any arm, there is more than 95% chance that p is greater than 30%, ie, stop the trial if $\text{Prob}(p > 20\% \mid \text{data}) > 0.95$. For each arm, assuming a beta (1, 1) prior and applying the above stopping rule when every 10 patients have been treated and evaluated after 1-year follow-up, the stopping boundaries are as follows: The trial will be stopped if for any one of the two arms, $[\# \text{ patients with AE}] / [\# \text{ patients evaluated at 6 months}] \geq 6/10, 10/20, 14/30, 17/40, 21/50, 24/60$.

Osteonecrosis, primarily in the jaw, has been reported in patients treated with bisphosphonates. Most cases have been in cancer patients undergoing dental procedures, but some have occurred in patients with postmenopausal osteoporosis or other diagnoses. All patients will have dental screening for jaw osteonecrosis at baseline and every 6 months thereafter. Patients with recent tooth extraction and signs of incomplete healing and/or uncontrolled infection will be excluded. During the trial, any dental condition should be treated immediately but conservatively, avoiding any invasive surgical procedure.

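### Ibandronate doses 2 to 4 do not depend on any calcium or creatinine result, so a patient who falls past an entry limit can be re-dosed within the plan

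*Combined protocol and SAP*

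**What the plan says.** Section 4.0 fixes the infusions by calendar: "Ibandronate 3 mg intravenously over 15-30 seconds for 4 doses at 0-1.5, 3, 6, and 9 months". Item 2 of the same section lists the routine laboratory tests: "calcium, magnesium, alkaline phosphatase, albumin, and creatinine at baseline and at 3, 6, 9, and 12 months (± 4 weeks) post-transplant". In Table 1 the row "Routine lab : Ca, Mg, albumin, Cr, Alk phos" is marked at every visit where the intravenous drug is marked, and also at month 12. The table gives no order between draw and dose.

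Two limits bear on whether a patient is fit for the drug. Both are exclusion criteria in Section 3.2. Item 2 reads "Patients with hypocalcemia of less than 8.4 (corrected to account for the albumin level" and item 6 reads "Renal insufficiency (calculated creatinine clearance < 30 ml/min". Neither is repeated elsewhere as a condition of dosing.

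Section 5.2 contains a stopping rule for the whole trial, built on the event "the percent reduction in BMD is greater than or equal to 15% from baseline to 6 months", together with dental precautions. Section 5.5 lets the study team arrange an infusion in the home physician's office and attaches no laboratory requirement. In both arms, "all patients will receive 500 mg of elemental calcium carbonate and Vitamin D Analog 400 IU orally twice daily for 12 months".

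**The concern.** The protocol judges that patients beyond these calcium and renal limits should not enter. It gives no reason why the same state would be acceptable at month 3, 6 or 9. The population is also unstable. Section 2.0 says that more than half develop graft-versus-host disease needing prolonged immunosuppression, and Section 5.0 allows for 40% drop-out from death and relapse. A check at entry cannot stand for nine months of dosing.

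At stake is patient safety. The tests that would show the problem are already scheduled, but the plan does not say that anyone must see them before the dose or what to do if a value is out of range. The gap matters most off site, where the person giving the drug may not have the study results.

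**Working it through.** The plan states no figure on this point to reproduce. The check is a comparison of sections, followed by the timing that the windows allow.

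**Step 1. Does any section make a dose depend on a result?**

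- 3.2 items 2 and 6: limits at entry only.
- 4.0, treatment: dose dates by calendar. The only wording about holding anything concerns daily vitamin D.
- 4.0 item 2: the tests stand in a list of data and blood to be collected, with no review step.
- Table 1: tests and doses share visit columns, with no order.
- 5.2: a trial-level rule on bone density and dental screening. No per-patient rule on calcium or creatinine.
- 5.3: the package insert is named only to define which events are unexpected.
- 5.5: off-site infusion with no laboratory condition.

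None does.

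**Step 2. Can a compliant draw come after the dose?**

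Assumptions: 3 months = 91 days, 4 weeks = 28 days, and each dose is given on its due date, because no dose window is stated. The month 3 laboratory window is 91 - 28 = day 63 to 91 + 28 = day 119 after transplant.

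*Doses counted from transplant* (Section 4.0 and the shared columns of Table 1). Dose 2 is on day 91, so the latest compliant draw is 119 - 91 = 28 days after it.

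*Doses counted from dose 1* (the three-month interval in Section 5.5). With dose 1 on day d, dose 2 is on day d + 91. The start is day 21-45 in Table 1 and day 21-60 in Section 1.1.

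| Dose 1 (day) | Dose 2 (day) | Month 3 result relative to dose 2 |
|---|---|---|
| 21 | 112 | latest draw 119 - 112 = 7 days after |
| 28 | 119 | latest draw on the day of the dose |
| 45 | 136 | 136 - 119 = 17 to 136 - 63 = 73 days old |
| 60 | 151 | 151 - 119 = 32 to 151 - 63 = 88 days old |

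Doses 3 and 4 and their laboratory windows each move on by 91 days, so the offsets are the same. Depending on the calendar, the draw can follow the dose or be several weeks old. The missing review and hold rule does not depend on which calendar is meant.

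**Step 3. Can the scheduled draw serve as a pre-dose test?**

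Require the draw within 28 days before the infusion. On the transplant calendar, days 63 to 91 lie inside the laboratory window. On the dose-1 calendar, the look-back opens on day d + 91 - 28 = d + 63 and must open by day 119, so d can be at most 56. With dose 1 on day 60, the look-back is day 123 to 151, wholly after day 119. For such late starts the draw has to move with the infusion.

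**Step 4. How close could doses come if a held dose is given late?**

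If a held dose may be given up to 28 days late and the next dose is never early, the shortest gap among doses 2, 3 and 4 is 91 - 28 = 63 days, or 9 weeks. Holding dose 2 can only lengthen its gap from dose 1.

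**The case against.** The strongest reply is that the plan calls these tests routine monitoring and puts them at the dosing visits, so clinicians will naturally look at them. Table 1 does make review possible, and the 28-day case is the extreme of the window. But possible is not required, and the reply is weakest for off-site infusions.

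A second reply is that all patients take calcium and vitamin D. That addresses low calcium, not a fall in creatinine clearance.

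A third is that the two limits are entry criteria for both arms and are nowhere called dosing limits. That stands: using them for dosing is a proposal, though one that takes the protocol's own thresholds. The documents also name only osteonecrosis as a bisphosphonate harm, so the harm from re-dosing is inferred from the exclusions.

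A fourth is that the rule may be written elsewhere. The appendices were not available to this review, and the only one cited is Appendix F, the randomization scheme. Other clinical chemistry may also be done in ordinary care.

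A reader might also infer a count of infusions at risk. From "a maximum of 200 patients will be enrolled into the study" and equal allocation, 100 patients would have 100 × 3 = 300 later infusions, or 60 × 3 = 180 if 40% drop out before dose 2. These are all later infusions, not infusions given to patients past a limit. The documents do not support reading them as affected doses.

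**Conclusion.** The point holds as a gap in the written plan. Doses 2 to 4 are not conditional on any laboratory result, the laboratory window allows the draw to follow the dose, and off-site dosing carries no laboratory condition. Following the plan exactly permits re-dosing a patient whose values would have barred entry.

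The size is unknown. The documents give no frequency for crossing either limit, so no count is claimed. Nor do they support inferring that results go unread in practice or that patients will be harmed. The timing figures rest on 91-day quarters and doses given on their due dates; the main conclusion rests on neither. It is limited to the text reviewed, without appendices. It is a cheap improvement.

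**What to change.** In Section 4.0 item 2, Table 1 and Section 5.5, for the ibandronate arm:

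1. Take the already scheduled month 3, 6 and 9 calcium, albumin and creatinine before that visit's infusion, and no more than 4 weeks before it. Where the start date puts the infusion outside the post-transplant laboratory window, let the draw move with the infusion.
2. Have the study team review the results before each dose, including before it releases an off-site infusion.
3. Hold the dose if corrected calcium is below 8.4 or calculated creatinine clearance is below 30 ml/min, and repeat the test.
4. Give a held dose only if both values are within limits within 4 weeks after its due date; otherwise skip it.
5. Give later doses no earlier than their scheduled dates, which keeps doses 2, 3 and 4 at least about 9 weeks apart. A looser rule, allowing the held dose at any time before the next one, could put two 3 mg doses days apart and should be avoided.

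The change is protocol wording and adds no scheduled test. The cost is an occasional delayed or omitted dose, a repeat test when a dose is held, and some local blood draws for off-site infusions.
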